5.1.2.3 Management Guidelines

Table 1Guidelines for Management of Risks, Adverse Events, and
Selected Laboratory Abnormalities with Alectinib

Event	Action to Be Taken	
All AEs related ^a to alectinib (unless otherwise specified in this table) + hepatotoxicity AEs (irrespective of relatedness)	Grade 4: Femporarily interrupt alectinib for a maximum of 21 days after which the drug must be permanently withdrawn. If improvement o Grade ≤ 1 or baseline does not occur within 3 weeks, bermanently discontinue alectinib. First episode: If improvement to Grade ≤ 1 or baseline within 21 days, decrease the current dose of alectinib by 150 mg 1 capsule) BID. Second episode: If improvement to Grade ≤ 1 or baseline within 21 days, decrease the current dose of alectinib by another 150 mg (1 capsule) BID. Third episode: Permanently discontinue alectinib. Please note that dose should not be reduced below 300 mg BID. Grade 3: Temporarily interrupt alectinib for a maximum of 21 days after which drug must be permanently withdrawn. First episode: If improvement to Grade ≤ 1 or baseline occurs within 10 days alectinib may be restarted at the original dose or dose reduced by 150 mg (1 capsule) at the investigator's discretion. If improvement to Grade ≤ 1 or baseline occurs after 10 days but within 21 days then alectinib dose must be decreased by 150 mg (1 capsule BID). Second episode: If improvement to Grade ≤ 1 or baseline occurs within 10 days alectinib may be restarted at the original dose or dose reduced by 150 mg (1 capsule) at the investigator's discretion. If improvement to Grade ≤ 1 or baseline occurs after 10 days but within 21 days then alectinib dose must be decreased by 150 mg (1 capsule BID). Second episode: If improvement to Grade ≤ 1 or baseline occurs within 21 days, decrease the current dose of alectinib by 150 mg (1 capsule) BID. Third episode: Permanently discontinue alectinib. Grade 2: To be managed at the investigator's discretion. Please note that alectinib cannot be interrupted for more than 21 days and cannot be dose reduced below 300 mg BID. Grade 1: No action required	
Interstitial lung disease/ pneumonitis	Patients should be monitored for pulmonary symptoms indicative of interstitial lung disease/pneumonitis.	
	Regardless of relatedness to alectinib , study drug should be permanently discontinued in patients diagnosed with interstitial lung disease/pneumonitis of any grade.	
Hepatotoxicity	Liver test laboratory abnormalities are to be reported as AEs only if fulfilling the criteria listed in Section 5.3.5.4 and Section 5.3.5.6. At any time during the study treatment, if symptoms compatible with liver injury are observed, liver enzymes should be measured as soon as possible.	

Event	Action to Be Taken	
Hepatotoxicity (cont.)	Regardless of relatedness to alectinib , the grade-dependent rules for dose interruptions and dose modification outlined in the first section of this table must be followed.	
	In addition, study drug treatment has to be permanently discontinued if any of the following occurs:	
	• First observation of ALT or AST >8 × ULN	
	 ALT or AST >5× ULN for more than 2 weeks 	
	 First observation of ALT or AST >3× ULN and total bilirubin >2×ULN 	
	 First observation of ALT or AST >3× ULN and the appearance of jaundice or signs of hepatic dysfunction or other symptoms (such as fatigue, nausea, vomiting, right upper quadrant pain or tenderness, fever, rash, or eosinophilia [>5%]) 	
	 Following study drug discontinuation, weekly monitoring of laboratory values should continue until the abnormal values have normalized to pretreatment levels and/or an adequate explanation of the abnormal value is found 	
	 Resumption of study drug is not allowed in patients discontinuing because of any of the above criteria 	
Gastrointestinal tract AEs (e.g., nausea, vomiting, diarrhea, stomatitis)	The events are expected to be minimized by taking the study drug with a meal. If GI events occur, appropriate measures should be taken in accordance with local clinical practice guidelines.	
	In case of AEs related to alectinib, follow the grade-dependent rules for dose interruption and modification outlined in the first section of this table.	
Skin disorder AEs (e.g., phototoxicity, rash)	 Patients should be advised to avoid prolonged sun exposure while taking alectinib and for at least 7 days after study drug discontinuation. Patients should also be advised to use a broad-spectrum sunscreen and lip balm of at least SPF 50 to help protect against potential sunburn during this period. In case of AEs related to alectinib, follow the grade-dependent rules for dose interruption and modification outlined in the first section of this table. 	
Vision disorders	Investigators should consider referring the patients for an ophthalmologic evaluation according to local clinical practice guidelines if vision disorders persist or worsen in severity and to advise patients to exercise caution when driving or operating machinery due to the risk of developing a vision disorder.	
	In case of AEs related to alectinib, follow the grade-dependent rules for dose interruption and modification outlined in the first section of this table.	

Table 1Guidelines for Management of Risks, Adverse Events, and
Selected Laboratory Abnormalities with Alectinib (cont.)

Table 1Guidelines for Management of Risks, Adverse Events, and
Selected Laboratory Abnormalities with Alectinib (cont.)

Event	Action to Be Taken	
Edema	Physical examinations will be performed routinely in clinical trials In case edema events occur, appropriate measures should be ta in accordance with local clinical practice guidelines.	
	In case of AEs related to alectinib, follow the grade-dependent rules for dose interruption and modification outlined in the first section of this table.	
Abnormal renal function AEs	Kidney function laboratory abnormalities are to be reported as AEs if they fulfill the criteria listed in Section 5.3.5.4.	
	If at any time during the study treatment serum creatinine increases by $\ge 2 \times$ over the baseline-visit value, the patient has to be carefully monitored. All underlying factors that may have acutely impacted serum creatinine levels need to be evaluated and corrected (e.g., dehydration, recent exposure to contrast media, increased amount of cooked meat in diet, concomitant medications affecting renal function as appropriate, etc.).	
	Any serum creatinine value that is increased by $\ge 2 \times$ over the baseline-visit value requires repeat testing.	
	• For Grade 1 and Grade 2 AEs related to alectinib, follow the grade-dependent rules for dose interruption and modification outlined in the first section of this table.	
	• For Grade 3 AEs related to alectinib, temporarily interrupt alectinib until serum creatinine recovers to Grade 1 or baseline, then resume at reduced dose.	
	• For Grade 4 AEs related to alectinib, permanently discontinue study drug.	
Severe myalgia and CPK elevations	CPK laboratory abnormalities are to be reported as AEs if they fulfill the criteria listed in Section $5.3.5.4$.	
	Myopathy should be considered in any patient with diffuse myalgia, muscle tenderness or weakness, and/or marked elevations of CPK levels. Patients should promptly report unexplained muscle pain, tenderness, or weakness, particularly if accompanied by malaise or fever. CPK levels should be monitored in patients reporting these symptoms.	
	In case of AEs related to alectinib, follow the grade-dependent rules for dose interruption and modification outlined in the first section of this table.	

Table 1	Guidelines for Management of Risks, Adverse Events, a		
	Selected Laboratory Abnormalities with Alectinib (cont.)		

Bradycardia ^b	Grade 2 or Grade 3	
	 Temporarily withhold for a maximum of 21 days (after which the drug must be permanently withdrawn) until recovery to ≤ Grade 1 (asymptomatic) bradycardia or to a heart rate of ≥ 60 bpm. Evaluate concomitant medicinal products known to cause bradycardia, as well as anti-hypertensive medicinal products. If a contributing concomitant medicinal product is identified and discontinued, or its dose is adjusted, resume at previous dose upon recovery to ≤ Grade 1 (asymptomatic) bradycardia, or to a heart rate of ≥ 60 bpm. 	
	If no contributing concomitant medicinal product is identified, or if contributing concomitant medicinal products are not discontinued or dose modified, resume at reduced dose upon recovery to \leq Grade 1 (asymptomatic) bradycardia or to a heart rate of \geq 60 bpm.	
	Grade 4	
	 Permanently discontinue if no contributing concomitant medicinal product is identified. 	
	 If a contributing concomitant medicinal product is identified and discontinued, or its dose is adjusted, resume at reduced dose upon recovery to ≤ Grade 1 (asymptomatic) bradycardia or to a heart rate of ≥ 60 bpm within 21 days, with frequent monitoring as clinically indicated. 	
	Permanently discontinue in case of recurrence.	
Hemolytic anemia	If hemoglobin concentration is $<10 \text{ g/dl}$ (Grade ≥ 2) and hemolyti anemia is suspected, withhold alectinib and initiate appropriate laboratory testing in accordance with local clinical practice guidelines. If hemolytic anemia is confirmed, resume alectinib at a reduced dose (see the general dose modification table, Section 5.1.2.1) upon resolution with improvement of hemoglobin to Grade ≤ 1 or baseline, or permanently discontinue alectinib. In case of anemia of non-hemolytic mechanism, assessed as related to alectinib, follow the grade-dependent rules for dose interruption and modification outlined in the first section of this table.	

AE = adverse event; BID = twice a day; CPK = creatine phosphokinase; GI = gastrointestinal; ULN = upper limit of normal.

Note: Diarrhea, nausea, and vomiting should be handled with best supportive care first before considering dose modification. Preexisting pleural effusion will not be considered as an adverse event.

- ^a Please refer to Section 5.3.4 to determine whether event should be assessed as related or unrelated.
- ^b Heart rate less than 60 bpm.

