 - At least 4 weeks must have elapsed since the last dose of the prior cytotoxic chemotherapy or antibody-directed therapy.
 - At least 7 days must have elapsed since prior tyrosine kinase inhibitor therapy.
 - At least 14 days must have elapsed since prior radiotherapy.
- Measurable disease at baseline, as assessed by investigator (by RECIST v1.1, or according to RANO criteria for patients with primary CNS tumors)

For primary CNS tumors, only MRI scans will be accepted. If the local radiology facility cannot perform MRI, the patient will be excluded from the study.

- Life expectancy of at least 12 weeks in the opinion of the investigator
- Eastern Cooperative Oncology Group Performance Status of 0-2
- Adequate hematologic function:
 - Platelet count \geq 100 × 10⁹/L

Alectinib—F. Hoffmann-La Roche Ltd

17/Protocol BO41929, Version 4

- Absolute neutrophil count \geq 1500/µL
- Hemoglobin $\ge 9 \text{ g/dL}$
- Adequate hepatic function:
 - ALT (SGPT) and AST (SGOT) \leq 2.5 × upper limit of normal (ULN) (\leq 5 × ULN for patients with concurrent liver metastasis)
 - Bilirubin ≤2 mg/dL
- Adequate renal function:
 - Serum creatinine < 2 × ULN
 - Calculated creatinine clearance of ≥ 60 mL/min (Cockroft-Gault formula)
- Patients with primary CNS tumors are eligible
- Patients with CUP tumors are eligible
- Patient with brain or leptomeningeal metastasis are allowed in the study if asymptomatic and if they meet the following criteria:
 - No neurological signs and clinically stable for at least 2 weeks without corticosteroid treatment for brain metastasis prior to first dose of alectinib
 - If previously treated with whole-brain radiotherapy or gamma-knife radiosurgery, treatment must have been completed at least 2 weeks prior to first dose of alectinib
- Willingness and ability to comply with scheduled visits, treatment plans, laboratory tests and other study procedures
- Willingness to comply with home-based approach and visits by mHCPs
- Ability to swallow alectinib capsules intact (without chewing, crushing, or opening)
- Women of childbearing potential must have a negative serum pregnancy test result during screening and a negative urine pregnancy test at baseline before first dose of study drug is administered (unless a negative serum test was obtained within 10 days of first dose of study drug, in which case the urine pregnancy test is not required)

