Alectinib was approved in the United States, Canada, the European Union, and several other countries at a dose of 600 mg twice a day (BID) for the treatment of patients with ALK-positive metastatic NSCLC who have progressed on or are intolerant to crizotinib. This indication was approved by the FDA on the basis of the ORR and DOR observed in two single-arm pivotal studies (NP28761 and NP28673), demonstrating a combined ORR of 51% in this crizotinib-failed population and median DOR of 14.9 months (Yang et al. 2017). Efficacy in the CNS was also assessed in these trials, with a combined CNS response rate of 64% observed in patients with measurable CNS disease at baseline (Gadgeel et al. 2016). The most common adverse events (occurring in >20% of patients) observed in the combined analysis were constipation (38%), fatigue (34%), peripheral edema (28%), myalgia (25%), nausea (23%), cough (21%) and headache (21%). Reported adverse events were mostly of Grade 1 or Grade 2 severity, and no Grade \geq 3 adverse event occurred with a frequency of more than 5%, the most common being increased blood CPK (4%), dyspnea (4%), increased ALT (3%), and increased AST (3%). Adverse events leading to dose modification or interruptions occurred in 33% of patients, whereas adverse events leading to treatment withdrawal were reported in 6% of patients (Yang et al. 2017).

Alectinib—F. Hoffmann-La Roche Ltd 26/Protocol BO41929, Version 4

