4.1.1 Inclusion Criteria

Patients must meet the following criteria for study entry:

- Signed Informed Consent Form
- Age ≥ 18 years at time of signing Informed Consent Form
- Histologically confirmed locally advanced or metastatic solid tumor excluding lung cancer
- ALK-positive tumor per FMI NGS (NGS F1CDx, F1LCDx, or F1HEME) or per local accredited laboratory using validated NGS testing of tumor tissue or peripheral blood:
 - ALK fusion
 - The following ALK-activating mutations: R1275Q, F1245C, or F1174X
 - Local ALK test report (only for cases with local ALK testing; see Section 4.6.5.3)
- Disease progression on prior treatment, or previously untreated disease with no available acceptable treatment
- Other prior cancer therapies are allowed, including investigational drugs, if any treatment-related toxicities (excluding alopecia) have resolved to Grade 1 or better and laboratory values as defined in inclusion criteria, and meet the following washout criteria prior to first dose of alectinib:
 - At least 4 weeks must have elapsed since the last dose of the prior cytotoxic chemotherapy or antibody-directed therapy.
 - At least 7 days must have elapsed since prior tyrosine kinase inhibitor (TKI) therapy.
 - At least 14 days must have elapsed since prior radiotherapy.
- Measurable disease at baseline, as assessed by investigator (by RECIST v1.1, or according to RANO criteria for patients with primary CNS tumors)
 - For primary CNS tumors, only MRI scans will be accepted. If the local radiology facility cannot perform MRI, the patient will be excluded from the study.
- Life expectancy of at least 12 weeks in the opinion of the investigator
- Eastern Cooperative Oncology Group (ECOG) Performance Status of 0–2 (see Appendix 3)
- Adequate hematologic function:
 - Platelet count \geq 100 \times 10⁹/L
 - Absolute neutrophil count \geq 1500/µL
 - Hemoglobin \geq 9 g/dL
- Adequate hepatic function:
 - ALT (SGPT) and AST (SGOT) $\leq 2.5 \times$ upper limit of normal (ULN) ($\leq 5 \times$ ULN for patients with concurrent liver metastasis)
 - Bilirubin ≤2 mg/dL

Alectinib—F. Hoffmann-La Roche Ltd 42/Protocol BO41929, Version 4

- Adequate renal function:
 - Serum creatinine $< 2 \times ULN$
 - Calculated creatinine clearance of ≥ 60 mL/min (Cockcroft-Gault formula)
- Patients with primary CNS tumors are eligible
- Patients with CUP tumors are eligible

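### For patients with liver metastasis admitted at ALT/AST above 3 and up to 5 × ULN, the enzyme part of a permanent-stop criterion is already met at entry, so a new common symptom alone can end treatment

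*Protocol*

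**What the plan says.** **Entry.** Protocol Section 4.1.1 caps ALT and AST at 2.5 × ULN, with a separate ceiling for one subgroup. The synopsis gives the same exception: "5 × ULN for patients with concurrent liver metastasis".

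**Stopping.** The hepatotoxicity row of Table 1 (Section 5.1.2.3) first applies the table's grade-dependent rules, whatever the relationship to alectinib. It then adds a separate list under which "study drug treatment has to be permanently discontinued if any of the following occurs". One item on that list is "First observation of ALT or AST >3× ULN and the appearance of jaundice", signs of hepatic dysfunction, or other symptoms, with the symptoms illustrated as "such as fatigue, nausea, vomiting, right upper quadrant pain or tenderness, fever, rash, or eosinophilia". The row ends: "Resumption of study drug is not allowed in patients discontinuing because of any of the above criteria". Section 4.7.1 makes any event meeting the Section 5.1.2 stopping criteria a mandatory reason for permanent discontinuation.

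**Reference point.** This item is written purely in multiples of ULN. It mentions neither the entry value nor treatment emergence, and it makes no exception for patients admitted above 3 × ULN.

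**The concern.** The 5 × ULN ceiling is a deliberate exception for patients with liver metastasis. For those who use the upper part of it, the enzyme part of the symptom-based criterion no longer discriminates, because it is satisfied before the first dose. Only the symptom part remains, and the listed symptoms include common ones. Protocol Section 1.2.2 reports fatigue in 34% and nausea in 23% of patients in the pooled alectinib studies in lung cancer.

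Two outcomes are possible, and neither is good. A site that follows the text literally permanently withdraws a patient whose liver tests are no worse than the protocol accepted at enrolment. A site that assumes an unwritten baseline reference departs from a mandatory liver safety rule in patients who already have raised enzymes. Different sites may choose differently, which would also make the SAP Section 5.6.2 summary of adverse events leading to withdrawal harder to interpret. Liver enzymes are checked 2 weeks after baseline (Appendix 1, footnote h) and the first on-study scan is at 8 weeks, so the criterion can apply before any response has been assessed.

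**Working it through.** No sample-size or power figure enters the main point. The check sets the thresholds side by side.

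**1. Entry ceiling against each item in the permanent-stop list** (ceilings from Section 4.1.1, stopping items from Table 1)

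| Stopping item | Liver metastasis, entry ≤ 5 × ULN | No liver metastasis, entry ≤ 2.5 × ULN |
|---|---|---|
| ALT/AST > 8 × ULN | Not met: 5 < 8 | Not met |
| ALT/AST > 5 × ULN for more than 2 weeks | Not met: 5 is not above 5 | Not met |
| ALT/AST > 3 × ULN and bilirubin > 2 × ULN | Enzyme part met for values > 3 to 5; bilirubin part not met (step 2) | Not met: 2.5 < 3 |
| ALT/AST > 3 × ULN and jaundice, hepatic signs or symptoms | **Enzyme part met for values > 3 to 5** | Not met: 2.5 < 3 |

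**2. Bilirubin.** Entry requires bilirubin of at most 2 mg/dL. The documents give no bilirubin ULN. If it is 1.0 to 1.3 mg/dL (an assumption), the entry cap is 2/1.0 = 2.0 down to 2/1.3 = 1.5 × ULN, so bilirubin above 2 × ULN is not met at entry. The problem is confined to the symptom-based item in patients with liver metastasis who enter above 3 and up to 5 × ULN.

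**3. What happens on treatment.** Take a patient admitted at 4 × ULN whose value falls to 3.5 × ULN. The enzyme part is still met. If fatigue or nausea newly appears, the text requires a permanent stop without resumption, although the enzymes have improved.

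**4. How related rules handle the reference point**
- Table 1, grade-dependent rules: recovery to Grade 1 or lower, or to baseline.
- Table 1, renal row: creatinine relative to the baseline-visit value.
- Section 5.3.5.6, liver event reporting: treatment-emergent ALT/AST above 3 × ULN.
- SAP Section 5.6.3, Hy's Law analysis: ALT/AST above 3 × the baseline value.
- Table 1, symptom-based stopping item: none.

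**5. Possible size of the effect on the primary endpoint.** The number of patients entering at 3 to 5 × ULN is not in the documents. As an illustration only, assume 2 to 6 of the 50 fusion patients, and assume that the 34% fatigue rate carries over:
- stops through fatigue: 0.34 × 2 = 0.68 to 0.34 × 6 = 2.04;
- expected responders among them at the planned 46%: 0.46 × 0.68 = 0.31 to 0.46 × 2.04 = 0.94.

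The plan's own figure reproduces: 23/50 has a Clopper-Pearson lower limit of 31.81%. For 22/50 it is 29.99%, just below the 30% that SAP Section 5.3.2 requires the limit to exceed. One response is 1/50 = 2 percentage points.

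**The case against.** The strongest defence is that the criterion describes events during treatment. It speaks of study drug treatment, of something that occurs, and of the appearance of signs or symptoms. A long-standing symptom does not appear. The same row points to Section 5.3.5.6, which is limited to treatment-emergent values, and refers to symptoms compatible with liver injury. Section 5.3.5.8 counts a preexisting condition as an adverse event only if it worsens. The row is plainly aimed at emerging liver injury, and a composite rule naturally uses a lower enzyme threshold once symptoms are added.

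Much of this stands, and it rules out three stronger readings that a reader might infer:

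- **That an eligible patient meets the stopping rule at baseline.** On the natural reading only the enzyme part is met at entry, and the symptom must be new. Fatigue at entry is not excluded, since ECOG 0 to 2 and residual Grade 1 toxicity are allowed, but calling this a Day 1 stop means disregarding the requirement that the symptom appear.
- **That the two sections cannot both be followed.** They can: enrol at 4 × ULN, then stop when a symptom appears. The difficulty lies in what that produces. The instruction to stop regardless of relatedness also belongs to the grade-dependent rules, not expressly to the permanent-stop list.
- **That the primary result is threatened.** The 2 to 6 patients are assumed. The 34% is any fatigue in lung cancer studies, not new fatigue coinciding with raised enzymes. Stopping drug does not make a patient a non-responder: the estimand is treatment policy (SAP Section 1.1.1), and scans continue with every effort to confirm a response (Protocol Sections 4.6.5 and 4.7.1). The step from 31.81% to 29.99% applies to any single lost response and says nothing specific about this rule.

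What the defence does not supply is a qualifier. The surrounding text suggests the intent but does not amend the stopping item, and even when the symptom must be new, the unchanged-enzyme case in step 3 remains.

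**Conclusion.** The concern holds in a limited form. For patients with liver metastasis admitted above 3 and up to 5 × ULN, and for no others, the enzyme part of the symptom-based criterion is met from entry. A new symptom such as fatigue or nausea, with enzymes unchanged or falling, then requires permanent discontinuation without resumption. This follows from the protocol's own thresholds and needs no assumption about numbers.

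The number of affected patients cannot be derived from the documents. The illustration gives at most about one expected responder among those stopped (0.3 to 0.9), and not every stop loses a response. These patients stay in the response-evaluable population, so the planned 50 and the stated power do not change. The effect on the response rate is indirect and probably small. The point rests on consistent application of a liver safety rule and on avoidable permanent discontinuations. It should be addressed, because the gap is in a mandatory rule and is cheap to close.

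**What to change.** Reconcile Section 4.1.1 and the matching synopsis text with the Table 1 hepatotoxicity stopping criteria. State explicitly how the criterion of ALT/AST above 3 × ULN plus symptoms applies to patients admitted above 3 × ULN, including whether a value already known at screening counts as a first observation and whether the symptom must be new on treatment. Which threshold or reference point applies is for the sponsor's clinical team, and none is proposed here.

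The cost is clarifying wording in the protocol. No visits, samples or procedures are added, and the sample size and primary analysis are unaffected.
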